4.4 Data Monitoring Committee (DMC) Activities

An independent external Data Monitoring Committee (DMC) is used to review unblinded safety data at regular intervals during the conduct of the study. The DMC will provide recommendation to an AbbVie Point of Contact on whether to continue, modify, or terminate studies after each review. When needed, high-level unblinded efficacy data may also be requested by the DMC and be reviewed so that the DMC can assess benefit:risk of any emerging safety differences.

5.0 Analysis Populations and Analysis Windows

5.1 Analysis Populations

Open-Label Treated Population

The open-label treated population consists of all subjects who have received at least one dose of open-label study medication. It will be used for all long-term efficacy, safety, and baseline analysis.

5.2 Definition of Baseline

The baseline value will be determined by the last non-missing measurement recorded on or before the date of the first dose of study drug in RCT. This applies to both efficacy and safety analysis.

5.3 Analysis Windows

Definition of OL-Rx Days (Days Relative to the First Dose of Open-Label Study Drug)

For the purpose of defining analysis windows for the open-label study, OL-Rx Days are calculated for each time point relative to the first dose of open-label study drug. They are defined as the number of days between the day of the first dose of open-label study drug and the specific time point. OL-Rx days are negative values when the time point of interest is prior to the first dose day of the open-label study drug, while OL-Rx days are positive values when the time point of interest is on or after the first dose day of open-label study drug. The day of the first dose of open-label study drug is defined as OL-Rx Day 1, while the day immediately prior to the first dose day of open-label study drug is defined as OL-Rx Day –1 (there is no OL-Rx Day 0). OL-Rx days are used to map actual study visits to the protocol specified study visits.

Definition of Analysis Windows

The following rules will be applied to assign actual subject visits to protocol-specified visits. For each protocol-specified study visit, a target study day will be identified to represent the corresponding visit along with a window around the target day. Windows will be selected in a non-overlapping fashion so that a collection date does not fall into multiple visit windows. If a subject has two or more actual visits in one visit window, the visit closest to the target day will be used for analysis. If two visits are equidistant from the target day, then the later visit will be used for analysis.

The visit window and the target OL-Rx day for each protocol-specified visit are displayed in [Table 1](#).

Table 1. Analysis Windows for Efficacy, Laboratory Assessments and Vital Signs

Protocol Specified Visit Week	Lower Bound	Target Day^a	Upper Bound
Baseline	Last non-missing measurement recorded on or before the date of the first dose of study drug in RCT		
6	2	43	64
12	65	85	127
24	128	169	211
36	212	253	295
48	296	337	379
60	380	421	463
72	464	505	547
84	548	589	631
96	632	673	715
108	716	757	799
120	800	841	883
132	884	925	967
144	968	1009	1051
156	1052	1093	1135
168	1136	1177	1219
180	1220	1261	1303
192	1304	1345	1387
204	1388	1429	1471
216	1472	1513	1555
228	1556	1597	1639
240	1640	1681	1723
252	1724	1765	1807
264	1808	1849	1891
276	1892	1933	1975
288	1976	2017	2059
300	2060	2101	2143
312	2144	2185	2227

a. Relative to the day of first dose of open-label study drug.

6.0 Demographics, Baseline Characteristics, Medical History, and Previous/Concomitant Medications

6.1 Demographic and Baseline Characteristics

The demographic data and baseline characteristics will be reported for the Baseline visit of the preceding RCT Studies M13-537 and M13-550. Demographic and baseline characteristics will be summarized for the Open-Label Treated Population. The number of observations, mean, standard deviation, median, minimum and maximum will be summarized for continuous variables. Categorical or discrete variables will be summarized via frequencies and percentages. The summary statistics will be computed for each treatment group, and the combined upadacitinib group.

Main Demographic and Baseline Characteristics

- Sex (male/female)
- Age (years)
- Age Categories (< 45, [45,65), ≥ 65 years)
- Race (White, Black, American Indian/Alaska Native, Native Hawaiian or Other Pacific Islander, Asian, Other)
- Geographic region (Western Europe, Eastern Europe, North America, South/Central America, Other)
- Ethnicity (Hispanic or Latino, Not Hispanic or Latino)
- Weight (kg)
- Weight Categories (< 60 kg, ≥ 60 kg)
- Height (cm)
- Body Mass Index (BMI) (kg/m²)
- Body Mass Index (BMI) Category (kg/m²) (< 18.5, [18.5,25), [25,30), ≥ 30)

RA Medical History and Characteristics

- Duration of RA in years
- Number of prior DMARDs used (for Study M13-537 subjects)

- MTX as first prior DMARD (Yes/No) (for Study M13-537 subjects)
- Number of prior biologic DMARD(s) used (for Study M13-550 subjects)
- Oral steroid use at baseline (yes, no)
- Oral steroid dose (prednisone equivalent) at baseline

Baseline RA Disease Characteristics

- Individual scores of each ACR component (e.g., hsCRP, SJC, TJC, etc.)
- DAS28 (CRP)
- DAS28 categories:
 - DAS28 > 5.1 (High Disease Activity)
 - DAS28 ≤ 5.1
- Clinical Disease Activity Index (CDAI) and categories:
 - CDAI > 22 (High Disease Activity)
 - CDAI ≤ 22
- Simplified Disease Activity Index (SDAI) and categories:
 - SDAI > 26 (High Disease Activity)
 - SDAI ≤ 26
- Anti-cyclic citrullinated peptide (Anti-CCP) (units)
- Anti-CCP status (Positive or Negative)
- Rheumatoid Factor (RF) (KU/L)
- RF status (Positive or Negative)

Patient Report Outcomes at Baseline

- Functional Assessment of Chronic Illness Therapy-Fatigue (FACIT-F)
- Work Instability Scale for Rheumatoid Arthritis (RA-WIS)
- EQ-5D-5L

Clinical Tests at Screening

- Chest x-ray
- ECG
- Tuberculin PPD skin test, QuantiFERON TB Gold test
- Serum pregnancy test

Immunization History

- BCG immunization
- Herpes Zoster immunization

Tobacco/Nicotine and Alcohol Use

- Tobacco/Nicotine Use [user, ex-user, non-user, unknown]
- Alcohol Use [drinker, ex-drinker, non-drinker, unknown]

6.2 Medical History

Medical history data (defined relative to the preceding RCT studies) will be summarized and presented for Open-Label Treated Population using body systems and conditions/diagnoses as captured on the CRF. The body systems will be presented in alphabetical order and the conditions/diagnoses will be presented in alphabetical order within each body system. The number and percentage of subjects with a particular condition/diagnosis will be summarized by treatment group sequence (defined in Section 9.1) as well total as for Open-Label Treated Population. Subjects reporting more than one condition/diagnosis within a body system will be counted only once for that body system. No statistical comparison will be performed for medical history reporting.

6.3 Previous Treatment and Concomitant Medications

Prior and concomitant medications will be summarized by treatment group sequence (defined in Section 9.1) as well as total for Open-Label Treated Population. A prior

medication is defined as any medication taken prior to the first dose of study drug in the preceding RCT study. This includes medications with a start date before the first study drug administration date, regardless of the end date of these medications. Medications taken on the day of the first dose of study drug are not counted as prior medications. A concomitant medication is defined as any medication, other than study drug, that started prior to the first dose of open-label study drug and continued to be taken after the first dose of open-label study drug or any medication that started after the first dose of open-label study drug and within 1 day of the last dose of study drug.

The number and percentage of subjects who received a prior or concomitant medication will be tabulated separately by the generic name assigned by the most current version of the World Health Organization (WHO) Drug Dictionary.

6.4 Protocol Deviations

Protocol deviations based on ICH deviation criteria are categorized as follows:

1. Those who entered the study even though they did not satisfy the entry criteria
2. Those who developed withdrawal criteria during the study and were not withdrawn
3. Those who received the wrong treatment or incorrect dose, and
4. Those who received an excluded or prohibited concomitant medication.

The protocol deviations listed above will be summarized and listed by treatment group sequence (defined in Section 9.1) as well as overall for the Open-Label Treated Population.

7.0 Patient Disposition

The number of subjects treated, completed or discontinued in the open-label treatment period will be summarized by treatment group sequence (defined in Section 9.1) as well as overall for the Open-Label Treated Population. The number of subjects discontinuing

from the open-label treatment period will also be summarized with the reasons for discontinuation collected from CRF by the following categories:

- Adverse event
- Withdrew consent
- Lost to follow-up
- Lack of efficacy
- Subject non-compliance
- Requires alternative (or prohibited) therapy
- COVID-19 infection
- COVID-19 logistical restrictions
- Other

8.0 Study Drug Exposure and Compliance

8.1 Study Drug Exposure

The duration of exposure to study drug in M13-538 will be summarized for the Open-Label Treated Population by the following groups:

1. Upadacitinib 6 mg BID/15 mg QD

This includes upadacitinib 6 mg BID or 15 mg QD exposure from subjects who never titrated, as well as the upadacitinib 6 mg BID or 15 mg QD exposure prior to dose titration for subjects who titrated (censored at the time of up titration to 12 mg BID/30 mg QD).

2. Upadacitinib 12 mg BID/30 mg QD

This includes upadacitinib 12 mg BID or 30 mg QD exposure for subjects who titrated up (censored at the time of down titration to 6 mg BID/15 mg QD for subjects who titrated up and back down).

3. Upadacitinib 6 mg BID/15 mg QD post down titration

This includes upadacitinib 6 mg BID/15 mg QD exposure after down titration for subjects who titrated up and back down.

4. Any upadacitinib

This includes any upadacitinib exposure in Study M13-538.

The first three exposure groups are mutually exclusive in terms of exposure, and the three groups combined is represented by the fourth group.

The duration of exposure to study drug will be summarized for each exposure group as specified above, with the number of subjects, mean, standard deviation, median, minimum and maximum values. In addition, the number and percentage of subjects exposed to study drug will be summarized for the following cumulative duration intervals.

Open-label exposure:

- ≥ 6 months
- ≥ 12 months
- ≥ 18 months
- ≥ 2 years
- ≥ 2.5 years
- ≥ 3 years
- ≥ 4 years
- ≥ 5 years

8.2 Compliance

Study drug compliance (TC) will be summarized for the Open-Label Treated Population. The treatment compliance is defined as the number of capsules/tablets taken (i.e., the difference between the number of capsules/tablets dispensed and the number of

capsules/tablets returned) during the subject's participation in the open-label treatment period divided by the number of capsules/tablets planned to be taken by the subject during the open-label treatment period of the study. In Study M13-538, subjects will switch from twice-daily formulation (capsules) to once-daily formulation (tablets). The impact of missing a once-daily tablet should be weighted twice as much as that for a twice-daily capsule. Specifically, TC will be calculated using the following formula:

$$TC = \frac{\text{number of twice daily capsules taken} + \text{number of once daily tablets taken} \times 2}{(\text{Number of days from first to last dose of open label study drug}) \times 2} \cdot 100\%$$

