## **5.5 Treatments**

### **5.5.1 Treatments Administered**

Treatments administered during this OLE include upadacitinib 6 mg BID, 12 mg BID, (15 mg QD or 30 mg QD from January 2017). All subjects start treatment with 6 mg BID. Dose adjustments are allowed as described in Section 5.1.

Subject receiving 6 mg BID will dose with two 3 mg capsules twice a day.

Subjects receiving 12 mg BID will dose with one 12 mg capsule twice a day.

Subject receiving 15 mg QD will dose with one 15 mg tablet once a day.

Subject receiving 30 mg QD will dose with one 30 mg tablet once a day.

Study drug will be taken orally beginning at Baseline/Week 0 in OLE. Subjects will be instructed to take study drug at approximately the same times each day. The study drug can be taken with or without food. Subjects will continue their weekly stable dose of MTX and folic acid. AbbVie will not supply MTX or folic acid.

If a subject is unable to come to the study site to pick up their study drug due to state of emergency or any pandemic like COVID-19, a direct-to-patient (DTP) study drug shipment can be made from the study site to the subject if allowed by local regulations. AbbVie will submit any required notifications to the regulatory authority as applicable. Refer to Section 5.3.1.1 for details on DTP shipment of study drug.

Information about the Investigational Product is presented in Table 4.

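### The SAP 8.2 compliance formula counts every dose of the 6 mg BID starting regimen twice, so full adherence on it prints 200%

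*SAP*

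**What the plan says.** SAP 8.2 defines compliance (TC) in words and then in a formula.

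- **In words.** The amount taken is "the difference between the number of capsules/tablets dispensed and the number of" units returned. It is "divided by the number of capsules/tablets planned to be taken by the subject during the open-label treatment period of the study".
- **Weighting.** Because subjects move from capsules to tablets, the SAP adds: "The impact of missing a once-daily tablet should be weighted twice as much as that for a twice-daily capsule".
- **Formula.** The numerator is the "number of twice daily capsules taken" plus two times the once-daily tablets taken. The denominator is two times the "Number of days from first to last dose of open label study drug". The ratio is multiplied by 100%.

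Protocol 5.5.1 gives the regimens. For the lower capsule dose it says: "Subject receiving 6 mg BID will dose with two 3 mg capsules twice a day". That makes four capsules per day. For the higher capsule dose the wording is: "Subjects receiving 12 mg BID will dose with one 12 mg capsule twice a day". That makes two. Each once-daily regimen is one tablet a day. The same section states: "All subjects start treatment with 6 mg BID". Protocol Table 4 lists capsules of 3 mg and 12 mg only, so 6 mg BID cannot be taken as one capsule per dose.

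**The concern.** The formula gives every capsule weight 1 and plans two units a day on every regimen. That assumes one capsule per dose, which is true of 12 mg BID and false of 6 mg BID. The tablet weighting suggests that the intended unit was one of two daily doses. But the amount taken is a count of physical capsules, and nothing in SAP 8.2 converts by strength. The words and the formula also disagree: the planned number of capsules on 6 mg BID is four a day, not two.

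Two things follow. Compliance is overstated for every subject with 6 mg BID intake, by an amount that depends on how long that subject stayed on those capsules. Real under-dosing can also look like good compliance. Values near 200% would probably be noticed in an output check; values near 100% that hide missed doses would not.

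**Working it through.** The documents state no compliance percentage, so there is no figure to reproduce. The check evaluates the SAP formula with the protocol's capsule counts.

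**Inputs**

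- Units per day: from Protocol 5.5.1, as in the table below.
- Formula: TC = 100% × (capsules + 2 × tablets) / (2 × days), from SAP 8.2.
- Treatment of about 312 weeks, and tablets at Week 72 at the earliest (from January 2017): Protocol 5.1.
- Exit of non-responders on 12 mg BID at Week 12 (after up-titration at Week 6) or Week 18 (after up-titration at Week 12): Protocol 5.1.

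**Step 1. Full adherence, one regimen**

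| Regimen | Units taken per day | Formula, per day | Printed TC |
|---|---|---|---|
| 6 mg BID | 4 capsules | 4 / 2 | 200% |
| 12 mg BID | 2 capsules | 2 / 2 | 100% |
| 15 mg or 30 mg QD | 1 tablet | (2 × 1) / 2 | 100% |

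**Step 2. General size of the error**

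Let D be the open-label days, D6 the days on 6 mg BID capsules, f = D6/D, and a6 the adherence on those days. The 3 mg capsules taken are n3 = 4 × a6 × D6. Counting each as half a dose removes n3/2 from the numerator, so

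printed TC − dose-based TC = (n3 − n3/2) / (2D) = n3 / (4D) = a6 × f.

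This needs no assumption about adherence on the other regimens. If adherence is a throughout, printed TC = a × [4f + 2(1 − f)] / 2 = a(1 + f).

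**Step 3. Typical courses**

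Visits are taken as on schedule. The last four rows assume 312 weeks completed; tablets start at Week 72 unless stated.

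| Course | f | TC at a = 100% | a = 80% | a = 50% |
|---|---|---|---|---|
| 6 mg BID capsules only (leaves before tablets) | 1 | 200% | 160% | 100% |
| Up at Week 6, exit at Week 12 | 6/12 = 0.500 | 150% | 120% | 75% |
| Up at Week 12, exit at Week 18 | 12/18 = 0.667 | 167% | 133% | 83% |
| Never titrated | 72/312 = 0.231 | 123% | 98% | 62% |
| Never titrated, tablets at an assumed Week 132 | 132/312 = 0.423 | 142% | 114% | 71% |
| Up at Week 6, back down at an assumed Week 24 | (6 + 48)/312 = 0.173 | 117% | 94% | 59% |
| Up at Week 6, not down | 6/312 = 0.019 | 102% | 82% | 51% |

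**Step 4. Unequal adherence**

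Take 50% adherence over 72 weeks of 6 mg BID (504 days), then full adherence over 240 weeks of tablets (1,680 days); D = 2,184.

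- 3 mg capsules taken: 4 × 504 × 0.5 = 1,008. Tablets taken: 1,680.
- SAP formula: (1,008 + 2 × 1,680) / (2 × 2,184) = 4,368 / 4,368 = 100.0%.
- Each 3 mg capsule counted as half a dose: (504 + 3,360) / 4,368 = 88.5%.
- SAP's verbal definition, raw units taken over planned: (1,008 + 1,680) / (2,016 + 1,680) = 2,688 / 3,696 = 72.7%.

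The gap between the first two is 11.5 points, which equals a6 × f = 0.5 × 72/312. The third shows that the SAP's words and its formula define different quantities.

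**The case against.** The reading that would rescue the formula is that capsules there means doses. The text does not support it: the amount taken is dispensed minus returned, and Protocol 5.3.2.1 treats the two as different units when it asks for the number of capsules in each of the last two doses.

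The stronger objection is that little depends on TC. It is one descriptive summary. SAP 8.2 does not split it by treatment sequence, and Protocol section 8 plans no compliance analysis. Sites check diaries and bottles at each visit (Protocol 5.3.1.1 and 5.5.5), and discontinuation for non-compliance comes from the CRF (SAP 7.0). All of this stands, and it limits the severity. It does not make the specified figure correct.

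Four narrower points also stand:

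- The printed summary alone cannot be converted back to adherence, but f could probably be recovered for each subject from dispensing records and titration dates.
- Protocol-permitted interruptions stay in the denominator, so a subject who follows the protocol through one scores below 100% under either formula.
- The documents show that dispensed kits identify the drug; they do not state that returned capsules are counted by strength.
- Other repairs would also give 100% at full adherence, such as counting dosing occasions or using a denominator that varies by regimen.

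**Conclusion.** The formula is wrong as written and should be corrected. For any subject with 6 mg BID intake it overstates dose-based compliance by exactly a6 × f. That result rests only on the capsule counts in Protocol 5.5.1 and the SAP's physical count of units taken.

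On the courses tabulated, the excess at full adherence runs from 1.9 points (up-titrated at Week 6, 312 weeks) to 100 points (6 mg BID capsules only). At 80% adherence the range is 1.5 to 80 points. These ranges depend on the assumed switch weeks, completion and adherence. The documents do not give the distribution of f or of adherence, so the effect on the population summary cannot be stated.

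The damage stops at this summary. Exposure durations (SAP 8.1) and event rates per 100 patient-years (SAP 10.2.1) use days, and no endpoint, population or model uses TC.

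**What to change.** Count doses and keep the capsule strengths apart:

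TC = [(3 mg capsules taken) / 2 + (12 mg capsules taken) + 2 × (tablets taken)] / [2 × days from first to last open-label dose] × 100%.

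With no interruption of dosing, this gives 100% at full adherence on all four regimens and any mix of them, and it keeps the SAP's two-to-one tablet weighting.

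Reword the verbal definition to match, because the raw ratio of units taken to units planned agrees with this formula only when adherence is the same on every regimen. Say that TC counts doses: two 3 mg capsules or one 12 mg capsule make one dose, and one tablet counts as two. State also how days of protocol-permitted interruption are treated.

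The cost is one formula and its definition in SAP 8.2, and the program. New data are unlikely to be needed, since kit numbers encode the study drug (Protocol 5.5.1.1); confirm that returned capsules can be counted by strength. No dose or clinical rule changes.

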9.0 Efficacy Analysis

9.1 General Considerations

Long-term efficacy analysis will be performed on the Open-Label Treated Population by the treatment group sequences as defined below:

1. Upadacitinib never titrated (6 mg BID/15 mg QD),
2. Upadacitinib titrated up and not down (6 mg BID/15 mg QD to 12 mg BID/30 mg QD), and
3. Upadacitinib titrated up and down (6 mg BID/15 mg QD to 12 mg BID/30 mg QD and then back down to 6 mg BID/15 mg QD).

No statistical tests will be conducted; only descriptive statistics and confidence intervals will be provided. All data will be summarized based on As Observed data (defined in Section 9.1.1).

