## **8.0 Statistical Methods and Determination of Sample Size**

### **8.1 Statistical and Analytical Plans**

#### **8.1.1 Dataset for Analysis**

The analysis set consists of all subjects who enrolled into this OLE study and received at least one dose of open-label study medication upadacitinib. This analysis set will be the primary analysis population for both efficacy and safety evaluation.

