#### **8.1.5.2 Efficacy Analysis**

The efficacy analyses will be conducted with the analysis set described in Section 8.1.1 and the observed cases (OC). The OC analysis will not impute values for missing evaluations, and thus a subject who does not have an evaluation on a scheduled visit will be excluded from the OC analysis for that visit.

Frequencies and relative frequencies (percentages) of ACR20/50/70 will be summarized with 95% confidence intervals at each post-baseline time point.

The proportion of subjects achieving Low Disease Activity (LDA) or Clinical Remission (CR), and the proportion of subjects achieving CR will be evaluated at Weeks 6, 12, 24, 36, 48, 60, 72, 84, 96 and every 24 weeks thereafter until the end of the study.

Frequencies and relative frequencies will be reported with 95% confidence intervals by visit, and will be summarized based on DAS28 [CRP] and CDAI criteria respectively.

For each of the change from baseline measurement, namely, TJC, SJC, Patient's Global Assessment of Disease Activity, Physician's Global Assessment of Disease Activity, Patient's Assessment of Pain (VAS), HAQ-DI, hsCRP, DAS28 [CRP] disease activity score, and CDAI, the mean, standard deviation, median, and range will be reported at each post-baseline time point. For Patient Reported Outcomes variables including change from baseline analyses of FACIT, RA-WIS, and EQ-5D, the mean, standard deviation, median and range will be summarized by visit. Confidence intervals at an overall level of 95% will be provided.

The impact of time between completion of RCT and roll-over to OLE will be explored.

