3.0 Introduction

This statistical analysis plan (SAP) describes the statistical analyses to be completed by the Data and Statistical Science Department for upadacitinib Study M13-538. It provides details to further elaborate statistical methods as outlined in the protocol and describes analysis conventions to guide the statistical programming work.

Unless noted otherwise, all analyses will be performed using SAS version 9.2 or later (SAS Institute Inc., Cary, NC 27513) under the UNIX operating system.

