9.2 Long-Term Efficacy Analysis

Assessments to evaluate long-term efficacy will be analyzed for the following measures at Weeks 6, 12, 24, 36, 48, 60, 72, 84, 96 and every 12 weeks until Week 312.

- ACR20/50/70 response rates;
- Change from baseline in individual ACR components;
- Change from baseline in DAS28 (CRP);
- Change from baseline in CDAI and SDAI;
- Proportion of subjects achieving LDA and proportion of subjects achieving CR based on DAS28 (CRP), CDAI and SDAI criteria;
- Change from baseline in Patient Reported Outcomes, including FACIT-Fatigue Scale, RA-WIS, and EQ-5D;

Analyses will be based on As Observed (AO) data. Descriptive statistics will be provided for each treatment group sequence in the Open-Label Treated Population as defined in Section 9.1. These include the number of observations, mean, standard deviation, and 95% CI for continuous endpoints; and frequencies and percentages with 95% CI using normal approximation for binary endpoints. In addition, longitudinal analysis will be

performed using MMRM or GLMM as described in Section 9.1.1 for all endpoints for treatment sequences 1 and 2. Point estimates and 95% CI from the model will be provided. Plots over time will be provided.

Table 1 below provides the overview of the long-term efficacy analysis to be performed on different endpoints.

Table 2. Summary of Long-Term Efficacy Analysis

Measure of Interest	Analysis Method
Binary endpoints: 
 • ACR20 at each visit • ACR50 at each visit • ACR70 at each visit • LDA based on DAS28 (CRP) at each visit • LDA based on CDAI and SDAI at each visit • CR based on DAS28 (CRP) at each visit • CR based on CDAI and SDAI at each visit 	
 • Point estimate and 95% CI of the response rate for each treatment sequence • Point estimate and 95% CI of the response rate using GLMM model for treatment sequences 1 and 2 • Plots over time (for ACR responses and LDA/CR based on DAS28 and CDAI) • Imputation: AO • Population: open-label treated population

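### The SAP specifies by-visit efficacy only by titration sequence, with no total for the all-treated set on which the protocol bases its efficacy summaries

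*SAP*

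**What the plan says.** Protocol 8.1.1 defines one analysis set, all enrolled subjects with at least one open-label dose, and adds: "This analysis set will be the primary analysis population for both efficacy and safety evaluation". Protocol 8.1.5.2 runs efficacy on that set using observed cases. For ACR responses it says "Frequencies and relative frequencies (percentages) of ACR20/50/70 will be summarized with 95% confidence intervals at each post-baseline time point"; for changes from baseline, "the mean, standard deviation, median, and range will be reported at each post-baseline time point". No split by dose or titration is mentioned, and Protocol 5.5.2 states that subjects are not assigned to treatment groups. Efficacy is part of the primary objective (Protocol 4.0, SAP 4.1).

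The SAP describes its own role in section 3.0: "It provides details to further elaborate statistical methods as outlined in the protocol". Its efficacy sections then group the population three ways (never titrated; up and not down; up and down):

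- SAP 9.1: "Long-term efficacy analysis will be performed on the Open-Label Treated Population by the treatment group sequences as defined below".
- SAP 9.2: "Descriptive statistics will be provided for each treatment group sequence in the Open-Label Treated Population as defined in Section 9.1".
- SAP 9.2, on the longitudinal models: "performed using MMRM or GLMM as described in Section 9.1.1 for all endpoints for treatment sequences 1 and 2".

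Table 2 repeats this for binary and continuous endpoints. Its population line names the set being divided and adds no overall row.

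**The concern.** Followed literally, the SAP yields no efficacy estimate for the population that the protocol calls primary. A total cannot be taken as understood, because the SAP asks for one wherever it wants one: baseline (6.1), medical history (6.2), medications (6.3), deviations (6.4), disposition (7.0), exposure (8.1) and adverse event rates (10.1).

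The groups that are reported are not neutral divisions either. A subject's sequence is settled by what happens after baseline, partly by response and partly by safety, tolerability or investigator discretion, yet it labels that subject at every visit from Week 6. Curves with confidence intervals by sequence can then be taken for dose results when part of the separation comes from the rule that sorted the subjects.

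**Working it through.** **1. Count of planned estimates.** SAP Table 1 has post-baseline windows at Weeks 6 and 12, then every 12 weeks from 24 to 312: 2 + [(312 - 24)/12 + 1] = 2 + 25 = 27. With three sequences, an endpoint assessed at every visit, such as ACR20, has 27 x 3 = 81 descriptive estimates and 0 for all treated subjects. The main study states no power or precision figure to reproduce.

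**2. Overlap between titration triggers and endpoints.**

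| Trigger (Protocol 5.1) | Endpoint (SAP) | Relation |
|---|---|---|
| Week 6 or 12: less than 20% improvement from RCT Baseline in TJC/SJC; dose should be raised | ACR20 needs at least 20% in both counts (9.4.1), from the same baseline (5.2) | Whichever way the word both is read, at least one count has missed 20%, so ACR20 fails at that visit |
| From Week 6: CDAI > 10; dose may be raised | CDAI LDA is CDAI <= 10 (9.4.9) | Exact complements |

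**3. What can be rebuilt.** Re-escalation is not allowed, so the three sequences are exhaustive. With n_k subjects observed in sequence k and N = sum n_k:

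- rate: p = sum(n_k p_k)/N; mean: m = sum(n_k m_k)/N
- SD^2 = [sum((n_k - 1) s_k^2) + sum(n_k (m_k - m)^2)]/(N - 1)

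Model-based estimates cannot be pooled this way, because sequence 3 is outside the MMRM/GLMM.

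**4. Illustration at Week 6 (assumed inputs).** Let R = 0.60 be overall ACR20, t = 0.35 the share ever titrated up, and f the share failing the Week 6 joint counts and up-titrated (ACR20 = 0 by definition). All other titration is taken as unrelated to that visit's ACR20. No Protocol 5.1 joint-count withdrawal has yet occurred at this visit.

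Never = R/(1 - f); ever = [(t - f)/t] x R/(1 - f); gap = R f/[(1 - f) t].

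| f | Never | Ever | Gap (points) |
|---|---|---|---|
| 0.02 | 61.2% | 57.7% | 3.5 |
| 0.05 | 63.2% | 54.1% | 9.0 |
| 0.10 | 66.7% | 47.6% | 19.0 |

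Each pair pools back to 60%. At f = 0.05 the gap is 15.8 points with t = 0.20 and 6.3 with t = 0.50.

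**5. Illustration at later visits (assumed inputs, simulated).** The set-up was 1,000,000 subjects with an equicorrelated normal score at each visit. ACR20 is the top 60%, CDAI LDA the top 45%, and joint-count failure the bottom 10%. The dose is raised for joint-count failure at Weeks 6 and 12, and with 2% probability at each visit without LDA. Dose has no effect on response. The Protocol 5.1 withdrawal rules are applied: failure on the raised dose at Week 12 or Week 18, and failure at two consecutive scheduled visits after Week 12. Sequences 2 and 3 are pooled as ever titrated.

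| Within-subject correlation | 0.2 | 0.4 | 0.6 |
|---|---|---|---|
| Week 48 gap, never minus ever (points) | about 9 | about 17 | 25 to 26 |
| All-treated as observed, Week 48 | 61% | 63% | 64% |
| All-treated as observed, Week 312 | 65% | 69% | 71% |

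The true rate is 60% at every visit. Withdrawal narrows the gaps and also makes the all-treated as-observed rate drift upward.

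**The case against.** The strongest reply is that there is no explicit contradiction. Protocol 8.1.5.2 names a set and a data-handling rule and is silent on grouping, while Protocol 8.1.2 does ask for overall figures for subject accountability. The SAP keeps the protocol's population and subdivides it. That stands as far as it goes: the all-treated summary is inferred from a single ungrouped set in a study with no treatment groups. It remains the natural reading, and a sequence-only presentation does not deliver it.

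A second reply is that nothing is lost. A reader might infer that the all-treated result becomes unobtainable; step 3 shows that as-observed rates, means and SDs can be recovered. What goes missing is the pre-specified reporting of them. Protocol 8.1.5.2 also plans medians and ranges that SAP 9.2 does not list. That difference is minor and separate, and exists within each sequence too.

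Third, the risk of misreading as dose effects is limited: no tests are planned, the group labels describe themselves, and SAP 4.2 sets out the titration rules. This is fair, and it makes misreading the lesser harm.

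Fourth, simulating titration without withdrawal gives Week 48 gaps of about 12, 24 and 35 points, with the total fixed at 60%. A reader might adopt those figures. Protocol 5.1 does not support them, because it removes joint-count failures, including those on the raised dose.

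**Conclusion.** The gap is real and worth fixing. The SAP specifies no efficacy estimate, descriptive or model-based, for the protocol's primary analysis population. It reports efficacy only in groups formed partly by post-baseline response. That conclusion rests on comparing the two texts and needs no simulation.

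The amount of sorting cannot be known from the documents. The figures of about 9, 17 and 26 points at Week 48 rest on assumed response rates, correlations and titration probabilities and on no dose effect; a real benefit of up-titration would shrink them. Two further inferences should be resisted. The all-treated as-observed rate is not an unbiased long-term rate, since it drifts up as non-responders leave. Nor does the protocol require an all-subject mixed model: it plans no mixed model at all.

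**What to change.** In SAP 9.1, 9.2 and Table 2:

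1. Add an all-treated (Any upadacitinib) as-observed column with 95% CI for every efficacy endpoint and visit, identified as the summary that corresponds to Protocol 8.1.5.2.
2. Keep the sequence tables, labelled as groups defined by post-baseline response and tolerability and not intended for dose comparison.
3. State beside the all-treated column that later as-observed rates exclude discontinued subjects, including those withdrawn for lack of joint-count improvement, and so tend to read high.

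Two additions are optional: an MMRM/GLMM on all subjects without a sequence term, and a total in the by-visit laboratory and vital-sign mean-change tables. Adverse event rates already have an Any upadacitinib group.

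The cost is SAP wording and one column per efficacy table. No new data are needed, and no dose, titration or withdrawal rule changes.
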